Appendix 2: Clinical Laboratory Evaluations

Clinical Chemistry Panel (Fasted):	Complete Blood Count:	Other Tests:
Alanine aminotransferase	Hematocrit	Hemoglobin A1c
Albumin	Hemoglobin	Thyroid-stimulating hormone
Alkaline phosphatase	Mean corpuscular hemoglobin	
Amylase	Mean corpuscular hemoglobin concentration	
Aspartate aminotransferase	Mean corpuscular volume	
Bilirubin (direct and total)	Platelet count	
Blood urea nitrogen	Red blood cell (RBC) count	Activated partial thrombin time
Calcium	RBC distribution width	Partial thromboplastin time
Chloride	White blood cell (WBC) count	Prothrombin time
Cholesterol	WBC differential (percent and absolute):	International normalized ratio
Creatine kinase	Basophils	
Creatinine	Eosinophils	
Glucose	Lymphocytes	
Iron	Monocytes	
Lipase	Neutrophils	
Magnesium		Human immunodeficiency virus antibody
Phosphorus		Hepatitis B surface antigen
Potassium		Hepatitis C virus antibody
Sodium		
Total protein		
Triglycerides		
Uric acid		
Urine Drug Screen:	Urinalysis:	For Female Subjects only:
Including but not limited to the following:		Pregnancy test (serum qualitative)
Alcohol (ethanol) (breath test)	Bilirubin	Follicle-stimulating hormone (postmenopausal females only)
Amphetamines	Color and appearance	
Barbiturates	Glucose	
Benzodiazepines	Ketones	
Cannabinoids	Leukocyte esterase	
Cocaine (metabolite)	Nitrite	
Methadone	Occult blood	
Opiates	pH and specific gravity	
Phencyclidine	Protein	
Cotinine	Urobilinogen	
	Microscopic examination including bacteria, casts, crystals, epithelial cells, RBCs, and WBCs (if protein, leukocyte esterase, nitrite, or blood is positive)	

Appendix 3: Total Blood Volume

The following blood volumes will be withdrawn for each subject.

Purpose	Approximate Blood Volume per Sample (mL)	Maximum Number of Blood Samples	Approximate Total Volume (mL)
Serology	4	1	4
Hemoglobin A1c	4	1	4
Primary Pharmacokinetic (PK) Sampling	4	60	240
Clinical Laboratory Tests:			
Complete Blood Count	4	10	40
Clinical Chemistry	4	10	40
Coagulation Parameters	3	10	30
Serum Pregnancy Test (females only)	4	3	12
Serum Follicle-stimulating Hormone Test (postmenopausal females only)	4	2	8
Thyroid-stimulating Hormone	4	2	8
Total:			386 mL

Appendix 4: Schedule of Assessments

Study Procedures ^a	Screening (Days -29 to -2)	Check-in (Day -1)	Period 1			Period 2						Period 3				Follow-up Phone Call (EOS)
			Day 1	Day 2	Day 7	Day 8	Day 11	Day 12	Day 13	Day 18	Day 19	Day 22	Day 23	Day 24	Clinic Discharge/ EOT Day 30 or ET ^t	
Confined to the CRU		X	X	X	X	X	X	X	X	X	X	X	X	X	X	X
Inclusion/Exclusion Criteria	X	X														
Informed Consent	X															
Demographics	X															
Medical History	X	X ^b														
Height/Weight/BMI	X	X ^c														
Physical Examination^d	X	X	X					X					X		X	
12-Lead ECG^e	X	X	X	X		X		X	X		X		X	X	X	
Vital Signs^f	X	X	X	X		X		X	X		X		X	X	X	
HDYF? Inquiry^g	X	X	X	X		X		X	X		X		X	X	X	X
AEs/SAEs^h	X	X	X	X	X	X	X	X	X	X	X	X	X	X	X	X
LOXO-292 Dosingⁱ			X					X					X			
Ranitidine Dosing^j							X (Days 8 to 18, inclusive)									
Omeprazole Dosing^k													X (Days 19 to 29, inclusive)			
Primary PK Blood Samples^l			X (Days 1-8)				X (Days 12-19)				X (Days 23-29)					
Clinical Laboratory Evaluations^m	X	X		X	X		X		X	X		X		X	X	
Hepatitis and HIV Screen	X															
Hemoglobin A1c Testⁿ	X															
Drug Screen^o	X	X														
Prior and Concomitant Medications^p	X	X	X	X	X	X	X	X	X	X	X	X	X	X	X	X
Serum Pregnancy Test^q	X	X												X		

Follicle-Stimulating Hormone Test ^r	X	X												
Thyroid-Stimulating Hormone Test	X	X												

Abbreviations: AE = adverse event; BMI = body mass index; CK = creatine kinase; CRU = Clinical Research Unit; ECG = electrocardiogram; EOS = end of study; EOT = end of treatment; ET = early termination; HDYF? = How Do You Feel?; HIV = human immunodeficiency virus; ICF = Informed Consent Form; PE = physical examination; PK = pharmacokinetic; SAE = serious adverse event.

^a For details on study procedures, see [Section 7](#).

^b Interim medical history only.

^c Weight and BMI (based on Screening height) only.

^d A complete PE will be performed at Screening and EOT (or ET). An abbreviated PE will be performed at Check-in (Day -1) and 1 hour postdose on Days 1, 12, and 23 (1 hour post LOXO-292 dose).

^e Electrocardiograms will be collected after the subject has rested in the supine position for at least 10 minutes, and will be obtained prior to and as close as possible to the scheduled blood draws at Screening and Day -1, Day 1 (before LOXO-292 dosing), Day 2, Day 8 (before ranitidine dosing), Day 12 (before LOXO-292 dosing), Day 13, Day 19 (before omeprazole dosing), Day 23 (before LOXO-292 dosing), Day 24, and EOT (or ET).

^f Vital signs measurements (oral temperature, respiratory rate, and supine blood pressure and heart rate) will be obtained Screening and Day -1, Day 1 (before LOXO-292 dosing), Day 2, Day 8 (before ranitidine dosing), Day 12 (before LOXO-292 dosing), Day 13, Day 19 (before omeprazole dosing), Day 23 (before LOXO-292 dosing), Day 24, and EOT (or ET). Vital signs measurements should be carried out prior to and as close as possible to having blood drawn. Blood pressure and HR will be measured using the same arm for each reading after the subject has been supine for at least 5 minutes.

^g An HDYF? inquiry performed at Screening (after the ICF is signed), at Check-in (Day -1), at each postdose vital signs assessment, and at an appropriate time for all other days.

^h AEs and SAEs will be collected beginning at informed consent. AEs will be recorded throughout the study (ie, from signing of the ICF until EOS, or until ET if the subject discontinues from the study and does not complete a follow-up phone call), either as subject medical history (if the event is reported as beginning prior to signing of the ICF or if the event occurs prior to study drug administration on Day 1 and is assessed as not related to study procedures by the Investigator [or designee]) or as AEs (if the event occurs after signing of the ICF but prior to study drug administration on Day 1 and is assessed by the Investigator [or designee] as related to study procedures, or if the event occurs after study drug administration on Day 1 through EOT or ET regardless of relationship to study drug). From EOT or ET through EOS, only AEs assessed as related to study drug are to be recorded. All SAEs that develop from the time of ICF signing until EOS (or ET if the subject discontinues from the study and does not complete a follow-up phone call) are to be reported.

ⁱ LOXO-292 will be administered in the morning of Days 1 and 12, following a fast of 10 hours prior to and 4 hours after the LOXO-292 dose. On Day 23, LOXO-292 will be coadministered with omeprazole within 30 minutes of the start of a low-fat meal which will be entirely consumed within 30 minutes.

^j On Day 12, ranitidine will be administered 2 hours (\pm 10 minutes) after the LOXO-292 dose. On Days 8 - 11 and 13 - 18, the morning dose of ranitidine will be administered (with breakfast) approximately 2 hours (\pm 1 hour) after the planned or actual time of the Day 12 LOXO-292 dose and the evening dose of ranitidine will be administered (with a light meal/snack) approximately 10 hours (\pm 1 hour) prior to the planned or actual time of the Day 12 LOXO-292 dose.

^k On Day 23, omeprazole and a single oral dose of 160 mg of LOXO-292 will be coadministered within 30 minutes of the start of a low-fat meal, which will be entirely consumed within 30 minutes. On Days 19-22 and 24-29, omeprazole will be administered following a fast of 2 hours prior to and 1 hour after the omeprazole dose (Note: omeprazole will be administered at approximately the actual time of the Day 12 LOXO-292 dosing).

^l Primary PK blood samples will be collected prior to dosing (within 30 minutes) and 0.25, 0.5, 0.75, 1, 1.5, 2, 2.5, 3, 4, 6, 8, 12, 24, 48, 72, 96, 120, 144, and 168 hours after LOXO-292 administration on Days 1, 12, and 23 for Periods 1, 2, and 3, respectively. The allowed sampling window for PK blood samples will be the following: within 15 minutes prior to dosing for the predose sample timepoint; \pm 5 minutes for sampling timepoints within the first 12 hours; \pm 30 minutes for sampling timepoints > 12 hours < 36 hours; and \pm 60 minutes for the sampling timepoints ranging from 48 to 168 hours.

^m Clinical chemistry panel including CK (fasted at least 8 hours), coagulation parameters, complete blood count, and urinalysis will be performed at Screening, Check-in (Day -1), and Days 2, 7, 11 (before ranitidine dosing), 13, 18 (before ranitidine dosing), 22 (before omeprazole dosing), and 24; and at EOT (Day 30) or ET.

ⁿ Hemoglobin A1c test performed at Screening only.

^o Alcohol breath test and drugs of abuse urine test, including cotinine. Results from the alcohol and drug tests will be used to determine subject eligibility per the inclusion/exclusion criteria.

^p Prior and concomitant medication administration will be recorded beginning at informed consent. In addition, all Investigator-approved medications taken by a subject within 30 days prior to study drug administration for prescription medications, and 14 days prior to study drug administration for nonprescription medications, will be recorded on the subject's electronic Case Report Form.

^q Female subjects only.

^r Postmenopausal female subjects only.

^s EOT is defined as when the subject is released from the CRU following completion of all assessments through Day 30. ET is defined as when the subject is released from the CRU if the subject terminates the study early. Vital sign, ECG, and safety laboratory results for serum chemistry, hematology, coagulation, and urinalysis are to be available for review by the Investigator or designee prior to subject release from the CRU at the EOT or ET visit.

^t To be performed 7 days (\pm 2 days) following EOT or ET. EOS is defined as when the CRU contacts the subject by a follow-up phone call 7 days (\pm 2 days) after the EOT visit or ET visit to determine if any SAE or study drug-related AE has occurred since the EOT or ET visit. All subjects who received LOXO-292 (including subjects who are terminated early) will be contacted.

Letter of Administrative Change (LOAC) No. 2
An Open-Label, 3-Period, Fixed Sequence Study to Evaluate the Effect of an
H2 Antagonist and a Proton Pump Inhibitor on the Single Dose
Pharmacokinetics of LOXO-292 in Healthy Adult Subjects

Protocol Date: 20 June 2019
Letter of Administrative Change (LOAC) Effective Date: 10 July 2019

Sponsor Reference Number: LOXO-RET-19075
Covance Study Number: 8412-056
IND Number: 133193

PPD

Description of Changes:

The purpose of this LOAC is to amend the text in Section 12.1, *Inclusion Criteria*, Sub-Section 12.1.1, *All Subjects* of the Protocol (dated 20 Jun 2019) to include bilateral tubal ligation as an acceptable form of sterilization for female study participants.

Section 12.1, *Inclusion Criteria*, Sub-Section, 12.1.1 *All Subjects* of the Protocol will be revised as follows:

Females of nonchildbearing potential, defined as being permanently sterile (ie, due to hysterectomy, bilateral salpingectomy, bilateral oophorectomy, bilateral tubal ligation or confirmed tubal occlusion more than 6 months prior to study drug administration) or postmenopausal (defined as at least 12 months postcessation of menses without an alternative medical cause). Postmenopausal status will be confirmed with a screening serum FSH level ≥ 40 mIU/mL. All females must have a negative qualitative serum pregnancy test (serum human chorionic gonadotropin) at Screening and Check-in (Day -1)

Reason for Changes:

Bilateral tubal ligation was erroneously not listed as an acceptable form of sterilization for female study participants Section 12.1, *Inclusion Criteria*, Sub-Section 12.1.1, *All Subjects*, in the Protocol dated 20 June 2019.

INVESTIGATOR AGREEMENT

PPD

SPONSOR AGREEMENT

PPD

10-Jul-19 | 13:42:21 PDT

Date

[figure not shown]
[figure not shown]
Letter of Administrative Change (LOAC) No. 1
An Open-Label, 3-Period, Fixed Sequence Study to Evaluate the Effect of an
H2 Antagonist and a Proton Pump Inhibitor on the Single Dose
Pharmacokinetics of LOXO-292 in Healthy Adult Subjects

Protocol Date: 20 June 2019
Letter of Administrative Change (LOAC) Effective Date: 24 June 2019

Sponsor Reference Number: LOXO-RET-19075

Covance Study Number: 8412-056

IND Number: 133193

Description of Changes:

The purpose of this LOAC is to revise the name of the manufacturer of ranitidine included in Table 2 of Section 5.1, *Description, Storage, Packaging, and Labeling*, of the Protocol, dated 20 Jun 2019.

Table 2 of Section 5.1, *Description, Storage, Packaging, and Labeling* will be revised as follows:

Table 1 Study Drug – Period 2

Study Drug	LOXO-292	Ranitidine
Form	Capsule ^a	Tablet
Strength	80 mg	150 mg
Supplier	Loxo Oncology, Inc.	Covance
Manufacturer	Avista Pharma Solutions, Inc.	Amneal Pharmaceuticals, LLC.

^aSpecific ingredients/purity will be identified in the Certificate of Analysis (or equivalent) that is supplied with the study drug.

Reason for Changes:

Table 2 of Section 5.1, *Description, Storage, Packaging, and Labeling* lists the manufacturer of ranitidine 150 mg tablets as Ajanta Pharma Limited. The manufacturer of ranitidine 150 mg tablets to be used in this study is Amneal Pharmaceuticals, LLC.

INVESTIGATOR AGREEMENT

PPD

SPONSOR AGREEMENT

PPD

24-Jun-19 | 09:45:53 PDT

Date

3 ABBREVIATIONS

Abbreviations pertain to the SAP only (not the TFLs).

ADaM	analysis data model
AE	adverse event
ANOVA	analysis of variance
AUC _{0-∞}	area under the concentration-time curve from time 0 extrapolated to infinity
AUC _{0-t}	area under the concentration-time curve from time 0 to the time of last quantifiable concentration
%AUC _{extrap}	percentage of AUC that is due to extrapolation from the last measurable concentration to infinity
BID	twice daily
BLQ	below the level of quantification
CDISC	Clinical Data Interchange Standards Consortium
CL/F	apparent systemic clearance
C _{max}	maximum observed concentration
CSR	clinical study report
CV%	coefficient of variation
ECG	Electrocardiogram
ICH	International Conference on Harmonisation
λ _z	apparent terminal elimination rate constant
LLOQ	lower limit of quantification
LSM	least squares means
MedDRA	Medical Dictionary for Regulatory Activities
NC	not calculated
NR	no result
PK	Pharmacokinetic
PPI	Proton Pump Inhibitor
QD	every day
QTc	QT correction; QT interval corrected for heart rate
QTcF	QTc calculated using the Fridericia correction
SAE	serious Adverse Event
SAP	Statistical Analysis Plan

$t_{1/2}$	apparent terminal elimination half-life
t_{max}	time of maximum observed concentration
TEAE	treatment-emergent adverse event
TFLs	tables, figures, and listings
ULN	upper limit of normal
V_z/F	apparent volume of distribution

4 INTRODUCTION

This SAP has been developed after review of the clinical study protocol (Final Version 1 dated 20 June 2019).

This SAP describes the planned analysis of the safety, tolerability, and PK data from this study. A detailed description of the planned TFLs to be presented in the Clinical Study Report (CSR) is provided in the accompanying TFL shell document.

The intent of this document is to provide guidance for the statistical analyses of PK data. In general, the analyses are based on information from the protocol, unless they have been modified by agreement with Loxo Oncology, Inc. and Company. A limited amount of information concerning this study (eg, objectives, study design) is given to help the reader's interpretation. This SAP must be finalized prior to the lock of the clinical database for this study. When the SAP and TFL shells are agreed upon and finalized, they will serve as the template for this study's CSR.

This SAP supersedes the statistical considerations identified in the protocol; where considerations are substantially different, they will be so identified. If additional analyses are required to supplement the planned analyses described in this SAP, they may be performed and will be identified in the CSR. Any substantial deviations from this SAP will be agreed upon with Loxo Oncology, Inc. and identified in the CSR.

This SAP is written with consideration of the recommendations outlined in the International Conference on Harmonisation (ICH) E9 guideline entitled, "Guidance for Industry: Statistical Principles for Clinical Trials" and the ICH E3 guideline entitled, "Guidance for Industry: Structure and Content of Clinical Study Reports."^{1,2}

5 STUDY OBJECTIVES

5.1 Primary Objectives:

- To assess the effect of multiple doses of an H2 antagonist (ranitidine) administered with a single dose of LOXO-292 on the PK of LOXO-292 under fasted conditions in healthy adult subjects.
- To assess the effect of multiple doses of a PPI (omeprazole) administered with a single dose of LOXO-292 on the PK of LOXO-292 given with a low-fat meal in healthy adult subjects.

5.2 Secondary Objective:

- To determine the safety and tolerability of a single dose of LOXO-292 under fasted conditions alone, in combination with an H2 antagonist (ranitidine) under fasted conditions, and in combination with a PPI (omeprazole) given with a low-fat meal in healthy adult subjects.

6 STUDY DESIGN

This is an open label, 3-period, fixed sequence study.

In Period 1, a single oral dose of LOXO-292 will be administered under fasted conditions. On Day 1 of Period 1, a single oral dose of 160 mg of LOXO-292 will be administered following a fast of 10 hours prior to and 4 hours after the LOXO-292 dose. Blood samples for LOXO-292 PK analysis will be taken for 168 hours after the LOXO-292 dose on Day 1.

In Period 2, multiple oral doses of ranitidine will be administered twice daily from Day 8 until Day 18 inclusively (for a total of 11 consecutive days) and administered with a single oral dose of LOXO-292 on Day 12 under fasted conditions. On Day 12, a single oral dose of 160 mg of LOXO-292 will be administered following a fast of 10 hours prior to and 4 hours after the LOXO-292 dose. On Day 12, ranitidine will be administered 2 hours (\pm 10 minutes) after the LOXO-292 dose. On Days 8-11 and 13-18, the morning dose of ranitidine will be administered (with breakfast) approximately 2 hours (\pm 1 hour) after the planned or actual time of the Day 12 LOXO-292 dose and the evening dose of ranitidine will be administered (with a light meal/snack) approximately 10 hours (\pm 1 hour) prior to the planned or actual time of the Day 12 LOXO-292 dose. Blood samples for LOXO-292 PK analysis will be taken for 168 hours after the LOXO-292 dose on Day 12.

In Period 3, multiple oral doses of omeprazole will be administered once daily from Day 19 until Day 29 inclusively (for a total of 11 consecutive days) and administered with a single oral dose of LOXO-292 on Day 23 with a low-fat meal. On Day 23, omeprazole and a single oral dose of 160 mg of LOXO-292 will be coadministered within 30 minutes of the start of a low-fat meal, which will be entirely consumed within 30 minutes. On Days 19-22 and 24-29, omeprazole will be administered following a fast of 2 hours prior to and 1 hour after the omeprazole dose (Note: omeprazole will be administered at approximately the actual time of the Day 12 LOXO-292 dosing). Blood samples for LOXO-292 PK analysis will be taken for 168 hours after the LOXO-292 dose on Day 23.

There will be a washout period of 7 days between the LOXO-292 dose in Period 1 and the first dose of ranitidine in Period 2 and a washout period of 7 days between the LOXO-292 dose in Period 2 and the first dose of omeprazole in Period 3.

7 TREATMENTS

The following is a list of the study treatment sequence abbreviations and ordering that will be used in the baseline TFLs.

Study Treatment labels	Treatment Order on TFLs
Treatment sequence label	
160 mg LOXO-292/ 160 mg LOXO-292 + 150 mg ranitidine BID/ 160 mg LOXO-292 + 40 mg omeprazole QD	
Treatment labels	
160 mg LOXO-292	1
150 mg ranitidine BID	2
160 mg LOXO-292 + 150 mg ranitidine BID	3
40 mg omeprazole QD	4
160 mg LOXO-292 + 40 mg omeprazole QD	5
PK outputs	
160 mg LOXO-292 (fasted)	1
160 mg LOXO-292 (fasted) + 150 mg ranitidine BID	2
160 mg LOXO-292 (fed) + 40 mg omeprazole QD	3

8 SAMPLE SIZE JUSTIFICATION

CCI

9 DEFINITION OF ANALYSIS POPULATIONS

The **All Subjects Population** will consist of any subjects who signed informed consent and had study assessments recorded on the database as per the protocol.

The **Safety Population** will consist of all subjects who received at least 1 dose of LOXO-292.

The **Pharmacokinetic Population** will consist of all subjects who received a dose of LOXO-292, have at least 1 quantifiable plasma concentration, and for whom at least 1 PK parameter can be computed. A subject may be excluded from the PK summary statistics and statistical analysis if the subject has an adverse event (AE) of vomiting that occurs at or before 2 times median time to maximum concentration.

All protocol deviations that occur during the study will be considered prior to database lock for their severity/impact and will be taken into consideration when subjects are assigned to analysis populations. Details of subject assignment to the analysis populations will be listed.

10 STATISTICAL METHODOLOGY

10.1 General

Data listings will be provided for the All Subjects Population. Summary statistics and statistical analyses will be performed for subjects included in the relevant analysis populations (Safety/PK).

For continuous data, summary statistics will include the arithmetic mean, (arithmetic coefficient of variation (CV%) and standard error of the mean (SEM) for PK summaries), arithmetic standard deviation, median, minimum, maximum, and number. For log-normal data (eg, the PK parameters: areas under the concentration-time curve [AUCs] and maximum observed concentration [C_{max}]), the geometric mean and geometric coefficient of variation (CV%) will also be presented. For categorical data, frequency counts and percentages will be presented. Data listings will be provided for all subjects up to the point of withdrawal, with any subjects excluded from the relevant population highlighted. For the calculation of summary statistics and statistical analysis, unrounded data will be used.

Missing values will not be imputed.

Data analysis will be performed using SAS® Version 9.4.

Analysis Data Model (ADaM) datasets will be prepared using Clinical Data Interchange Standards Consortium (CDISC) ADaM Version 2.1, and CDISC ADaM Implementation Guide Version 1.1. Pinnacle 21 Community Validator Version 2.2.0 will be utilized to ensure compliance with CDISC standards.

10.1.1 Definition of Baseline and Change from Baseline

Baseline value is defined as the last non-missing measurement prior to the administration of LOXO-292 in each period, including repeats (vital signs and electrocardiograms [ECGs]) and unscheduled (clinical laboratory parameters) readings (see [Section 10.1.2](#) for definitions of repeat and unscheduled readings). LOXO-292 dosing days are: Day 1 (Period 1), Day 12 (Period 2) and Day 23 (Period 3).

Mean change from baseline is the mean of all individual subjects' change from baseline values. Each individual change from baseline will be calculated by subtracting the individual subject's baseline value from the value at the timepoint. The individual subject's change from baseline

values will be used to calculate the mean change from baseline using a SAS procedure such as Proc Univariate.

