10.4.3 Clinical Laboratory Parameters

Clinical chemistry, hematology and coagulation data will be summarized by parameter and treatment, together with changes from baseline. In addition, all clinical chemistry, hematology, coagulation and urinalysis data outside the clinical reference ranges will be listed by parameter and treatment.

Values for any clinical chemistry, hematology, coagulation and urinalysis values outside the clinical reference ranges will be flagged on the individual subject data listings.

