10.4.4 Vital Signs

The vital signs data will be summarized by treatment, together with changes from baseline. Vital signs values outside the clinical reference ranges will be flagged on the individual subject data listings.

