10.4.5 Electrocardiogram

The ECG data will be obtained directly from the 12-lead ECG tracings. These data include the QT interval calculated using the Fridericia correction (QTcF), the PR, RR and QT intervals, the QRS duration, and heart rate.

Changes from baseline will be calculated. Values for ECG parameters outside the clinical reference ranges will be flagged, including $QTcF > 450$ msec and change from baseline > 30 msec, on the individual subject data listings.

The ECG data will be summarized and listed by treatment, together with changes from baseline.

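### Does resetting the safety baseline before each LOXO-292 dose hide change on the ranitidine and omeprazole combinations?

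*SAP*

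**What the plan says.** SAP 10.1.1 defines one baseline per period: "Baseline value is defined as the last non-missing measurement prior to the administration of LOXO-292 in each period". It names Days 1, 12 and 23 as the dosing days. The Protocol Synopsis and Protocol 8.4 give the same rule.

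Changes from this baseline are reported for all three data types:
- Laboratory (SAP 10.4.3): "Clinical chemistry, hematology and coagulation data will be summarized by parameter and treatment, together with changes from baseline".
- Vital signs (SAP 10.4.4): "The vital signs data will be summarized by treatment, together with changes from baseline".
- ECG (SAP 10.4.5): "The ECG data will be summarized and listed by treatment, together with changes from baseline". The same section flags QTcF above 450 msec "and change from baseline > 30 msec, on the individual subject data listings".

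The secondary objective (SAP 5.2) is the safety and tolerability of one LOXO-292 dose by itself when fasted, "in combination with an H2 antagonist (ranitidine) under fasted conditions, and in combination with a PPI (omeprazole) given with a low-fat meal".

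SAP 7 gives five treatment labels, including ranitidine alone and omeprazole alone, with the "ordering that will be used in the baseline TFLs". The detailed layout of the outputs is "provided in the accompanying TFL shell document" (SAP 4). SAP 10.4.7 plans no inferential safety analysis.

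**The concern.** Ranitidine starts on Day 8 and omeprazole on Day 19. The Period 2 and Period 3 baselines are therefore not drug-free: each follows four days of the acid reducer. If QTcF, a laboratory value or blood pressure had already moved by Day 12 or Day 23, the change columns for the combinations would omit that movement. A QTcF rise of 35 msec from Day 1, made up of 10 before Day 12 and 25 after it, would receive no change flag.

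This matters at first sight because Protocol 1.2 lists possible QTc prolongation among the theoretical risks of LOXO-292, and Protocol 1.3 reports Grade 3 or higher QT prolongation in 2.8% of patients.

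A second worry is the two acid-reducer-alone labels. Their only scheduled on-drug readings are the baselines themselves: laboratory tests on Days 11 and 22, ECG and vital signs predose on Days 12 and 23. If the labels were used for these data, the change would be zero or empty. It would be reversed in sign if the Day 8 or Day 19 pre-drug readings carried them.

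**Working it through.** There is no sample-size or power figure to reproduce here. The check applies the plan's own rule to its own schedule.

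**1. The identity.** Change from Day 1 = (Day 12 or 23 predose − Day 1 predose) + (later reading − Day 12 or 23 predose) = earlier shift + period change. The period change omits exactly the earlier shift.

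**2. What the earlier shift can contain.**
- Acid reducer: 12 − 8 = 4 days of ranitidine; 23 − 19 = 4 days of omeprazole.
- Residual LOXO-292: doses are 11 days (264 h) apart. With the half-life of about 24 h in Protocol 1.3, 0.5^11 = 0.05% remains, which is negligible.
- Time: 11 days from Day 1 to Day 12, and 22 days from Day 1 to Day 23.

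**3. Effect on the QTcF flag.** It fires when period change > 30, that is, when the rise from Day 1 exceeds 30 + shift. The shifts below are assumed; the documents report none.

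| Earlier shift (msec) | −15 | −10 | −5 | 0 | +5 | +10 | +15 |
|---|---|---|---|---|---|---|---|
| Rise from Day 1 needed for a flag | >15 | >20 | >25 | >30 | >35 | >40 | >45 |

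With no shift the two versions agree.

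**4. How many readings are involved.** Protocol Appendix 4, footnote e, schedules 8 ECGs after Day 1 dosing: Days 2, 8 (predose), 12 (predose), 13, 19 (predose), 23 (predose), 24 and 30. With 20 completers, 8 × 20 = 160.
- If each reading is set against the latest preceding baseline: Days 2 and 8 against Day 1 (40); Days 13, 19, 24 and 30 against an on-acid-reducer value (80); Days 12 and 23 are baselines (40).
- If the Day 8 and Day 19 predose readings belong to the period that starts that day: 20 against Day 1 (Day 2), 60 against an on-acid-reducer value (Days 13, 24, 30), and 80 baseline or pre-baseline.

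**5. Is the shift lost?** No. Predose ECGs and vital signs are scheduled on Days 1, 12 and 23. For laboratory tests the corresponding scheduled readings are Days −1, 11 and 22. SAP 10.4.3 to 10.4.5 summarise observed values as well as changes, and Protocol 8.4 lists all safety data by subject. The earlier shift is one subtraction away, and the 450 msec flag does not depend on any baseline.

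**6. What a Day 1 reference would measure.** At the Day 23 predose reading it combines 22 days in the unit, 2 LOXO-292 doses, up to 11 × 2 = 22 ranitidine doses and 4 omeprazole doses. Blood drawn between the Day −1 and Day 22 laboratory tests is 2 × 80 mL of PK samples plus 5 safety sets of 4 + 4 + 3 = 11 mL: 160 + 55 = 215 mL, which matters for hematology.

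It also produces its own chance flags. In a simulation with assumed within-subject SDs of 6, 8 and 10 msec per reading, a true LOXO-292 effect of 10 msec and no earlier shift, 0.8%, 3.0% and 5.5% of subjects exceed 30 msec from Day 1 but not from the period baseline. All of that is noise. With an assumed true shift of 10 msec the figures are 11.4%, 16.5% and 19.3%.

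**7. The acid-reducer-alone labels.** Whether all five labels are used for laboratory, vital-sign and ECG tables depends on the shells, which are not among the documents. The only windows the SAP assigns to labels are those for adverse events in SAP 10.4.1. There, time up to predose Day 8 belongs to LOXO-292 alone, and time up to predose Day 19 to the ranitidine combination. Applied by analogy, the Day 8 and Day 19 predose readings would not carry an acid-reducer-alone label, so the sign reversal would not arise.

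**The case for a change.** The strongest opposing case is that no output described in the SAP shows or flags total change on the combinations, although the objective names them. QTcF is a recognised concern for this drug, every reading needed is already scheduled, and the words in Protocol 8.4 that allow a different baseline where specified would permit a second one. Specifying it before database lock would be cheap and would avoid a post hoc choice.

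The facts in that case stand. The period change is not total change, and a subject whose QTcF had drifted before Day 12 or Day 23 could be flagged or left unflagged because of the drift.

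What does not follow is that the plan is wrong. The grammatical subject of the objective is a single LOXO-292 dose. Total change since Day 1 is a different quantity, which neither document sets out to report. Nor do the documents give reason to expect a material shift: Protocol 1.5 anticipates no significant risk from either acid reducer at the doses used. In an uncontrolled fixed sequence, a change from Day 1 could not be attributed to the combination in any case.

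On the labels, ranitidine alone and omeprazole alone are outside the secondary objective, and an awkward zero or empty column would be a matter of table layout that these documents cannot settle.

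**Conclusion.** The concern does not hold. The per-period baseline is consistent across the Protocol Synopsis, Protocol 8.4 and SAP 10.1.1. It fits the secondary objective and gives sound descriptive output as written. Its known limitation is that it omits any shift before Day 12 or Day 23. This touches 60 to 80 of 160 post-dose ECG comparisons and moves the flag threshold, in terms of rise from Day 1, by exactly the size of that shift. The documents give no such shift, so the size of any real effect is unknown; it is zero apart from noise if there is none.

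Observed values, out-of-range flags, the 450 msec flag, adverse events and the primary PK analysis are unaffected, and no safety test is planned. A supplementary change from Day 1 is an option that a reasonable statistician could take or decline. This conclusion assumes that observed values are presented and listed as SAP 10.4.3 to 10.4.5 and Protocol 8.4 state. The point on the acid-reducer-alone labels cannot be judged without the shells and is not a fault in the plan.
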